5.5 FOLLOW-UP OF PATIENTS AFTER ADVERSE EVENTS

5.5.1 Investigator Follow-Up

The investigator should follow each adverse event until the event has resolved to baseline grade or better, the event is assessed as stable by the investigator, the patient is lost to follow-up, or the patient withdraws consent. Every effort should be made to follow all serious adverse events considered to be related to study treatment or trial-related procedures until a final outcome can be reported.

During the study period, resolution of adverse events (with dates) should be documented on the Adverse Event eCRF and in the patient's medical record to facilitate source data verification.

All pregnancies reported during the study should be followed until pregnancy outcome, with follow-up information on the infant collected according to procedures outlined in [Appendix 7](#) and [Appendix 8](#).

5.5.2 Sponsor Follow-Up

For serious adverse events, adverse events of special interest, and pregnancies, the Sponsor or a designee may follow up by telephone, fax, email, and/or a monitoring visit to obtain additional case details and outcome information (e.g., from hospital discharge summaries, consultant reports, autopsy reports) in order to perform an independent medical assessment of the reported case.

5.6 ADVERSE EVENTS THAT OCCUR AFTER THE ADVERSE EVENT REPORTING PERIOD

After the end of the reporting period for serious adverse events and adverse events of special interest (defined as days after the final dose of study treatment or until

initiation of new systemic anti-cancer therapy, whichever occurs first), all deaths, regardless of cause, should be reported through use of the Long-Term Survival Follow-Up eCRF.

In addition, if the investigator becomes aware of a serious adverse event that is believed to be related to prior exposure to study treatment, the event should be reported through use of the Adverse Event eCRF. However, if the EDC system is not available, the investigator should report these events directly to the Sponsor or its designee, either by faxing or by scanning and emailing the paper Clinical Trial Adverse Event/Special Situations Form using the fax number or email address provided to investigators.

5.7 EXPEDITED REPORTING TO HEALTH AUTHORITIES, INVESTIGATORS, INSTITUTIONAL REVIEW BOARDS, AND ETHICS COMMITTEES

The Sponsor will promptly evaluate all serious adverse events and adverse events of special interest against cumulative product experience to identify and expeditiously communicate possible new safety findings to investigators, IRBs, ECs, and applicable health authorities based on applicable legislation.

The Sponsor has a legal responsibility to notify regulatory authorities about the safety of a study treatment under clinical investigation. The Sponsor will comply with regulatory requirements for expedited safety reporting to regulatory authorities (which includes the use of applicable systems, such as EudraVigilance), IRBs, ECs, and investigators.

To determine reporting requirements for single adverse event cases, the Sponsor will assess the expectedness of these events through use of the reference safety information in the documents listed below:

Drug	Document
Atezolizumab	Atezolizumab Investigator's Brochure
Tiragolumab	Tiragolumab Investigator's Brochure

The Sponsor will compare the severity of each event and the cumulative event frequency reported for the study with the severity and frequency reported in the applicable reference document.

Reporting requirements will also be based on the investigator's assessment of causality and seriousness, with allowance for upgrading by the Sponsor as needed.

Certain adverse events are anticipated to occur in the study population at some frequency independent of study drug exposure and will be excluded from expedited reporting. Adverse events of special interest for each treatment arm are listed in the respective appendix for that treatment arm, as outlined in [Appendix 7](#) and [Appendix 8](#).

6. STATISTICAL CONSIDERATIONS AND ANALYSIS PLAN

The final study analysis will be based on patient data collected through study discontinuation. If not otherwise specified, efficacy analyses will be based on the efficacy-evaluable population, defined as all patients who receive at least one dose of each drug for their assigned treatment regimen, and safety analyses will be based on the safety-evaluable population, defined as all patients who receive any amount of study treatment.

The analysis results will be summarized by the treatment regimen that patients actually receive, as well as by stage (Stage 1 or Stage 2). Data will be described and summarized as warranted by sample size. Continuous variables will be summarized through use of means, standard deviations, medians, and ranges. Categorical variables will be summarized through use of counts and percentages. Listings will be used in lieu of tables in the event of small sample sizes.

New baseline values will be established for the Stage 2 efficacy and safety analyses. For evaluation of tumor response, new baseline tumor assessments will be established as described in Section 4.5.6. For other endpoints (e.g., change from baseline in vital signs or laboratory test results), the last non-missing value prior to a patient's first dose during Stage 2 will serve as the new baseline.

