4.2 METHOD OF TREATMENT ASSIGNMENT

This is a randomized, open-label study. After initial written informed consent has been obtained, all screening procedures and assessments have been completed, and eligibility has been established for a patient, the study site will obtain the patient's identification number and Stage 1 treatment assignment from the interactive voice or web-based response system (IxRS). Patients who enroll in Stage 2 will be assigned to treatment through use of the IxRS and will retain the same patient identification number that is assigned in Stage 1.

For Stage 1, this study will employ a permuted-block randomization method with dynamically changing randomization ratios to account for fluctuation in the number of treatment arms that are open for enrollment during the study. The randomization ratio will depend on the number of experimental arms that are open for enrollment (e.g., if an arm is added or enrollment in an arm is suspended pending analysis of results from the preliminary phase), with the stipulation that the likelihood of being allocated to the control arm will be no more than 50%. The randomization ratios may be altered to increase enrollment in a particular experimental arm that has demonstrated promising clinical activity.

Randomization will take into account general exclusion criteria and arm-specific exclusion criteria as outlined in Section 4.1.2. If a patient is eligible only for the control arm, the patient will not be enrolled in the study.

Patients who do not receive at least one dose of each drug for their assigned treatment regimen will not be included in the efficacy analyses. Additional patients may be enrolled in Stage 1 to reach the target number of treated patients planned for analysis.

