4.6.2 Patient Discontinuation from Study

Patients have the right to voluntarily withdraw from the study at any time for any reason. In addition, the investigator has the right to withdraw a patient from the study at any time.

Reasons for patient discontinuation from the study may include, but are not limited to, the following:

- Patient withdrawal of consent
- Study termination or site closure
- Adverse event
- Loss to follow-up
- Patient non-compliance, defined as failure to comply with protocol requirements as determined by the investigator or Sponsor

Every effort should be made to obtain information on patients who withdraw from the study. The primary reason for withdrawal from the study should be documented on the appropriate eCRF. Patients who withdraw from the study will not be replaced.

If a patient withdraws from the study, the study staff may use a public information source (e.g., county records) to obtain information about survival status.

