6.4 EFFICACY ANALYSES

6.4.1 Primary Efficacy Endpoint

The primary efficacy endpoint is objective response rate (ORR) (defined as the proportion of patients with an objective response [a complete or a partial response]) during Stage 1 based on RECIST v1.1, as defined in Section 2 (see Table 2). Patients with missing or no response assessments will be classified as non-responders.

ORR, the proportion of patients with a complete or partial response, will be calculated for each arm, along with 95% CIs (). The difference in ORR between the experimental arms and the control arm will also be calculated, along with 95% CIs using the with continuity correction.

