Appendix 8: Study Details Specific to Atezo + CAPOX + Tira Arm (cont.)

the placebo plus atezolizumab arm (n=29; 17.2% [95% CI: 1.8% to 32.7%]). Of note, responders in the tiragolumab plus atezolizumab arm included patients with both squamous and non-squamous histology.

In the ITT population, investigator-assessed PFS was improved in the tiragolumab plus atezolizumab arm compared with the placebo plus atezolizumab arm (stratified HR: 0.57 [95% CI: 0.37 to 0.90]; median PFS: 5.4 vs. 3.6 months, respectively). In the subgroup of patients with TPS \geq 50%, investigator-assessed PFS was improved in the tiragolumab plus atezolizumab arm compared with the placebo plus atezolizumab arm (unstratified HR: 0.33 [95% CI: 0.15 to 0.72]; median PFS: not estimable vs. 3.9 months, respectively).

As of the data cutoff date, most adverse events have been Grade 1 or Grade 2. Serious adverse events, Grade 3–5 adverse events, adverse events leading to discontinuation, and adverse events leading to death have been balanced between the two treatment arms. Serious and high-grade treatment-related adverse events have also been balanced between the two treatment arms. [REDACTED] have been balanced between the two treatment arms, with the exception of a higher frequency of infusion-related reaction (IRR) and rash reported in the atezolizumab plus tiragolumab arm.

[REDACTED]

Overall, tiragolumab in combination with atezolizumab has been well tolerated, adverse events have been manageable, and the safety profile seems to be consistent as reported across different solid tumor indications.

Refer to the Tiragolumab Investigator's Brochure for additional details on all ongoing and planned clinical studies.

A8–2.7 BENEFIT–RISK ASSESSMENT

Taking into account the potentially synergistic mechanisms of action of tiragolumab and atezolizumab, as well as the preliminary efficacy and manageable safety profiles of the above-described combinations, treatment with atezolizumab, CAPOX, and tiragolumab (Atezo + CAPOX + Tira) may have therapeutic potential in solid tumors such as GC and GEJC.

For the evaluation of the impact of the (coronavirus disease 2019) COVID-19 pandemic on the benefit–risk assessment, please refer to Section 1.4.

**A8–3 RATIONALE FOR DOSE AND SCHEDULE FOR
ATEZO+CAPOX+TIRA ARM**

[figure not shown]
A8–3.1 RATIONALE FOR ATEZOLIZUMAB DOSE AND SCHEDULE

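### Efficacy leaves out randomised patients who miss any one assigned drug, which can bias the planned ORR difference; all randomised patients should be the primary set

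*Combined protocol and SAP*

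**What the plan says.** Section 6 makes the efficacy-evaluable population the default for efficacy, "defined as all patients who receive at least one dose of each drug for their assigned treatment regimen". Section 4.2 states the consequence: "Patients who do not receive at least one dose of each drug for their assigned treatment regimen will not be included in the efficacy analyses". It then adds: "Additional patients may be enrolled in Stage 1 to reach the target number of treated patients planned for analysis". Section 4.6.2, on leaving the study, says: "Patients who withdraw from the study will not be replaced".

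For the primary endpoint, Section 6.4.1 says: "The difference in ORR between the experimental arms and the control arm will also be calculated". The difference comes with a 95% CI using a continuity correction; the name of the method is blacked out. The same section says: "Patients with missing or no response assessments will be classified as non-responders".

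Section 6.4.2 names no other population. It plans medians for PFS, OS and DOR, OS rates at fixed times and a disease control rate, all without a between-arm estimate. PFS and OS are timed from randomisation (Section 2, Table 2). On grouping, Section 6 says: "The analysis results will be summarized by the treatment regimen that patients actually receive".

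The readable text contains no all-randomised analysis, even as a sensitivity analysis. Section 6.9 (interim analyses) is blacked out and is not judged here.

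**The concern.** Randomisation protects the ORR difference only if being counted does not depend on what happens afterwards. Here it does. A patient who deteriorates, withdraws on learning the open-label allocation, or stops after an early infusion without ever receiving one of the drugs leaves both numerator and denominator. Such patients are plausibly less likely to respond than the rest. The non-responder rule in Section 6.4.1 was presumably meant to stop losses from flattering the result, but it works only inside the set that remains.

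What is at stake is the signal that the control arm was included to sharpen (Section 1.3). The experimental arm expands if clinical activity is seen in about 20 patients, with no numerical threshold in the readable text (Section 3.1.2). Randomisation ratios may also shift towards a promising arm (Section 4.2). At that size, one or two patients in the denominator can matter.

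**Working it through.** **1. The plan's own figure.** Table 4 gives the experimental arm 20 patients in the preliminary phase and 25 in the expansion. Assume 1:1 allocation, which fits the 50% cap on control with one experimental arm open. Then 2 × 20 = 40 and 2 × (20 + 25) = 90, which reproduces the stated 40–90. No power, type I error, effect size or exclusion rate is given.

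**2. The hurdle by arm.**
- Control (Appendix 7, Table 1): atezolizumab, capecitabine, oxaliplatin; three drugs.
- Experimental (Appendix 8, Table 1): the same plus tiragolumab; four drugs. In Cycle 1 tiragolumab starts 60 minutes after atezolizumab ends, and oxaliplatin follows tiragolumab (A8-4.1.2.2 and A8-4.1.2.3).
- If atezolizumab is stopped in control, CAPOX may continue (A7-5.1.4.2). If it is withheld or discontinued in the experimental arm, tiragolumab should be too, while CAPOX may continue (A8-5.1.5.2).

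Suppose a first atezolizumab infusion is started and then permanently stopped, and assume that a started infusion counts as a dose. A control patient who goes on to CAPOX stays in the efficacy set. An experimental patient with the same course never receives tiragolumab and is removed.

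**3. Formula.** Let p be the ORR in all patients randomised to an arm, f the fraction excluded and q the ORR among those excluded. The filtered ORR is (p − fq)/(1 − f), so the shift is f(p − q)/(1 − f). It is zero if q = p. If every excluded patient is a non-responder (q = 0), the filtered ORR is p/(1 − f). Top-up enrolment restores the count but does not undo the shift, because new patients pass through the same filter.

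**4. Numbers.** ORR and exclusions are assumptions. Responders are equal in both arms when all randomised patients are counted, and only experimental non-responders are dropped. The last three columns give the spurious difference in percentage points.

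| Per arm | Dropped | ORR 40% | ORR about 50% | ORR 60% |
|---|---|---|---|---|
| 20 | 1 | +2.1 | +2.6 | +3.2 |
| 20 | 2 | +4.4 | +5.6 | +6.7 |
| 45 | 3 | +2.9 | +3.5 | +4.3 |
| 45 | 5 | +5.0 | +6.1 | +7.5 |

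Example: 10/18 − 10/20 = 55.6% − 50.0% = +5.6 points. The middle column at 45 per arm uses 22/45 = 48.9%.

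**5. Precision.** A Wald interval with continuity correction is assumed: d ± {1.96 √[p₁(1−p₁)/n₁ + p₂(1−p₂)/n₂] + ½(1/n₁ + 1/n₂)}.
- 10/20 against 10/20: 1.96 × 0.158 + 0.050 = 0.360, so 0.0 (−36.0 to 36.0).
- 10/18 against 10/20: 1.96 × 0.162 + 0.053 = 0.370, so +5.6 (−31.5 to 42.6).
- 22/45 against 22/45: 0.0 (−22.9 to 22.9).

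**6. Other patterns, at ORR 50% with excluded patients all non-responders.**
- 10% excluded from each arm: both read 0.50/0.90 = 55.6% and the difference stays at 0.
- 10% excluded from the experimental arm and 5% from control: 55.6% − 52.6% = +2.9 points before rounding.
- Two dropped from control only, at 20 per arm: 10/20 − 10/18 = −5.6 points.

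**The case against.** The strongest defence is that this is a signal-finding study. Section 6.1 disclaims power and type I error, a set of treated patients is a natural choice for activity, and disposition is reported by arm (Section 6.2), so losses would be visible. A shift of a few points is small against half-widths of about 23 to 36 points. All of this stands, and it limits the severity. It does not justify the rule: a wide interval does not correct a systematic shift, and a disposition table does not change the estimate.

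Four stronger readings are tempting, but the documents do not support them.

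- **That the rule favours the experimental arm.** Appendix 8 reports "a higher frequency of infusion-related reaction (IRR) and rash reported in the atezolizumab plus tiragolumab arm", but in a different trial, in lung cancer without chemotherapy, and it concerns reactions rather than patients who never received a drug. A patient who reacts to tiragolumab has already started it. The rule sets no cycle limit, so a drug missed on the first day may be given later. Withdrawal after open-label allocation could equally thin the control arm.
- **That the PFS and OS comparisons are broken.** The readable text plans no hazard ratio, test or difference for them. What is affected is each arm's estimate, timed from randomisation but restricted to patients who later received every drug, and any informal comparison of those estimates.
- **That grouping by regimen received is a second major defect.** Everyone in the set has already received every assigned drug. An experimental patient who misses tiragolumab is excluded, not moved to control. In the main, only a control patient given tiragolumab in error would switch.
- **That Sections 4.2 and 4.6.2 contradict each other.** One concerns reaching a number treated, the other patients who leave the study. They overlap for a patient who withdraws before full dosing, and the wording should be reconciled, but a contradiction is not established.

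**Conclusion.** The concern holds for the ORR difference and for each arm's ORR. The rule filters patients after randomisation, in an open-label trial, with one more drug to receive in the experimental arm, and no all-randomised analysis stands beside it in the readable text.

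The direction and size are unknown. If ORR is 40–60%, every excluded patient is a non-responder and all exclusions fall in the experimental arm, one or two exclusions at 20 per arm create a spurious +2.1 to +6.7 points. Exclusions that are balanced in number and in response leave the difference unchanged; exclusions in control reverse the sign. With no hypothesis test planned, the harm is a possibly distorted activity signal, not an inflated error rate. This should be fixed because the remedy is cheap, not because the bias is shown to be large.

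**What to change.** In Sections 6 and 4.2:

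- Base ORR, the ORR difference, disease control, PFS and OS on all randomised Stage 1 patients, grouped by assigned arm.
- Count partly dosed patients by their actual RECIST assessments. Only missing or no assessments become non-response, which is the existing Section 6.4.1 rule and covers never-dosed patients without scans. Partial dosing should not itself be scored as failure, since both appendices allow treatment to continue without a component. For example, if one of 10 responders among 20 had missed a drug, scoring that patient as a failure would turn 10/20 = 50.0% into 9/20 = 45.0%.
- Keep the current efficacy-evaluable set as a sensitivity analysis, and report the number excluded from it, with reasons, by arm.
- Keep grouping by treatment received for safety.
- State how the top-up in Section 4.2 fits with the no-replacement statement in Section 4.6.2.

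The randomised total stays at 40–90. The cost is mainly wording, and ORR may read slightly lower. One operational gap must be closed: tumour assessments are timed from Day 1 of Cycle 1 (Section 4.5.6) and survival follow-up from treatment discontinuation (Section 4.6.1), so the readable text sets no schedule for never-dosed patients. Either follow them for survival or censor them at the last available date. For PFS, censor at randomisation if there is no post-baseline scan and no recorded death.

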6.1 DETERMINATION OF SAMPLE SIZE

This study is not designed to make explicit power and type I error considerations for a hypothesis test. Instead, this study is designed to obtain preliminary efficacy, safety, and PK data on immunotherapy-based treatment combinations when administered to patients with GC or GEJC. Cohort 1 will enroll patients with inoperable locally advanced, metastatic, or advanced GC or GEJC with adenocarcinoma confirmed as the predominant histology who have not received prior systemic therapy for advanced or metastatic disease.

Approximately 40-90 patients will be randomly allocated to the control and experimental arms during the study.

6.2 SUMMARIES OF CONDUCT OF STUDY

Enrollment will be summarized by region, country, and investigator by treatment arm in the two stages. Patient disposition will be summarized by treatment arm in each stage. Major protocol deviations, including major deviations with regard to the inclusion and exclusion criteria, will be summarized by treatment arm in each stage.

For safety-evaluable patients, study drug administration data will be tabulated or listed by treatment arm in each stage, and any dose modifications will be flagged. Means and

standard deviations will be used to summarize the total dose and dose intensity for each study drug. The reasons for discontinuation of study treatment will also be tabulated.

6.3 SUMMARIES OF DEMOGRAPHIC AND BASELINE CHARACTERISTICS

Demographic and baseline characteristics (including age, sex, race/ethnicity, weight, malignancy duration, metastatic disease site, and baseline ECOG Performance Status) will be summarized overall and by treatment arm in each stage.

6.4 EFFICACY ANALYSES

6.4.1 Primary Efficacy Endpoint

The primary efficacy endpoint is objective response rate (ORR) (defined as the proportion of patients with an objective response [a complete or a partial response]) during Stage 1 based on RECIST v1.1, as defined in Section 2 (see Table 2). Patients with missing or no response assessments will be classified as non-responders.

ORR, the proportion of patients with a complete or partial response, will be calculated for each arm, along with 95% CIs (). The difference in ORR between the experimental arms and the control arm will also be calculated, along with 95% CIs using the with continuity correction.

6.4.2 Secondary Efficacy Endpoints

The secondary efficacy endpoints are PFS, OS, OS at specific timepoints (e.g., 6 and 12 months), duration of response (DOR), and disease control during Stage 1, as defined in Section 2 (see Table 2). PFS, DOR, and disease control will be determined by the investigator according to RECIST v1.1.

DOR will be derived for efficacy-evaluable patients with a complete response or a partial response.

For patients who do not have documented disease progression or die, PFS and DOR will be censored at the day of the last tumor assessment.

Patients who are still alive at the time of OS analysis will be censored at the last date they were known to be alive.

The method will be used to estimate the median for PFS, OS, and DOR, with 95% CIs constructed through use of the method. The OS rate at specific timepoints will also be estimated using the method, with 95% CIs calculated based on for variance.

Disease control rate (the proportion of patients with stable disease for ≥ 12 weeks, a partial response, or a complete response) will be calculated for each treatment arm, with 95% CIs estimated using the [REDACTED].

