This Phase Ib/II umbrella study is designed to accelerate the development of treatment combinations by identifying early signals and establishing proof-of-concept clinical data in patients with GC or GEJC. The study is designed with the flexibility to open new treatment arms as new treatment combinations become available and close existing treatment arms that demonstrate minimal clinical activity or unacceptable toxicity. Enrollment of multiple experimental arms in a single study, rather than one or two experimental arms within multiple studies, will result in an overall reduction in the number of patients receiving control arm treatment. More importantly, this study will assess the importance of simultaneously targeting multiple pathways, including immune cell priming and activation, tumor infiltration, and/or recognition of tumor cells for elimination. To improve the confidence of clinical signal detection in the experimental arms, this study will include a control arm. In addition, patients who experience disease progression with the initial treatment regimen (Stage 1) may be eligible to continue treatment with a different treatment regimen (Stage 2), which may advance the scientific understanding of treatment resistance mechanisms in patients who do not respond to or experience disease progression during treatment.

This study will enroll patients with inoperable locally advanced, metastatic, or advanced GC or GEJC, with adenocarcinoma confirmed as the predominant histology, who have not received prior systemic therapy for their disease. Despite the recently demonstrated clinical benefit of nivolumab plus chemotherapy in patients with a PD-L1 CPS ≥ 5 , there remains a high unmet medical need for treatment-naïve patients with inoperable locally advanced, metastatic, or advanced GC or GEJC, requiring further evaluation of novel, more efficacious treatment combinations.

The target and proposed mechanism-of-action classification for each experimental investigational medicinal product (IMP) are presented in [Table 1](#). The control and experimental treatment regimens are described in Sections [3.1.1](#) and [3.1.2](#) (see [Table 4](#) and [Table 5](#)). Background information and a rationale for each treatment combination, including a benefit–risk assessment for experimental agent, are provided in the respective appendix for that treatment arm, as outlined in [Table 4](#) and [Table 5](#).

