Approximately 40-90 patients will be enrolled during Stage 1. Enrollment in the experimental arm will take place in two phases: a preliminary phase, followed by an expansion phase. For most arms, approximately 20 patients will be enrolled during the preliminary phase. If clinical activity is observed in the experimental arm during the preliminary phase, approximately 25 additional patients may be enrolled in that arm during the expansion phase. The Sponsor may decide to delay or suspend enrollment within a given treatment arm. If the experimental arm shows minimal clinical activity or unacceptable toxicity, then it will not undergo expansion. Additional patients may be enrolled to ensure balance across treatment arms with respect to demographic and baseline characteristics, including potential predictive biomarkers, to enable further subgroup analyses. New experimental arms may be added during the study by amending the protocol.

Patients in Stage 1 will be randomly assigned to experimental arms or the control arm, and the randomization ratio will depend on the number of experimental arms that are open for enrollment (e.g., if an arm is added or enrollment in an arm is suspended pending analysis of results from the preliminary phase), with the stipulation that the likelihood of being allocated to the control arm will be no more than 50%. The treatment regimen in the control arm may change with emerging data to reflect the evolving standard-of-care treatments; new control arm treatment will be updated by amending the protocol. Randomization will take into account arm-specific exclusion criteria. Patients will be ineligible for a specific arm if they meet any of the exclusion criteria outlined for that arm (see [Section 4.1.2](#)). Details on treatment assignment and randomization are provided in [Section 4.2](#).

[figure not shown]
Table 4 Stage 1 Treatment Regimens

Arm Name	Study Treatment ^a	Number of Patients		Appendix
		Preliminary Phase	Expansion Phase ^b	
Control (Atezo + CAPOX) ^c	Atezolizumab plus capecitabine plus oxaliplatin	Variable ^d		Appendix 7
Atezo + CAPOX + Tira	Atezolizumab plus capecitabine plus oxaliplatin plus tiragolumab	20	25	Appendix 8

Atezo = atezolizumab; CAPOX = capecitabine plus oxaliplatin; Tira = tiragolumab.

- ^a The Sponsor may decide to delay or suspend enrollment within a given treatment arm. Thus, all listed experimental arms may not be open for enrollment at the same time.

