After treatment discontinuation, information on survival follow-up and initiation of a new anti-cancer therapy will be collected by means of telephone calls, patient medical records, and/or clinic visits approximately every 3 months (± 2 weeks) or more frequently until death (unless the patient withdraws consent or the Sponsor terminates the study). If a patient requests to be withdrawn from follow-up, this request must be documented in the source documents and signed by the investigator. If the patient withdraws from the study, the study staff may use a public information source (e.g., county records) to obtain information about survival status only. For an experimental arm, in which all patients discontinued treatment and passed the safety follow-up window, as well as approximately 80% of patients discontinued the study, the Sponsor may conclude the arm (the remaining approximately 20% of patients will be discontinued from the study).

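### Section 6.4.2 plans no between-arm estimate for PFS or OS, although ORR gets one and the control arm is there to support signal detection

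*Combined protocol and SAP*

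**What the plan says.** - **Purpose of control.** Section 1.3: "To improve the confidence of clinical signal detection in the experimental arms, this study will include a control arm".
- **Endpoints.** Section 2, Table 2 makes PFS and OS secondary endpoints for Stage 1, both measured from randomisation.
- **ORR.** Section 6.4.1: "The difference in ORR between the experimental arms and the control arm will also be calculated", with a 95% CI.
- **PFS and OS.** In Section 6.4.2 a method whose name is blacked out "will be used to estimate the median for PFS, OS, and DOR", with 95% CIs. OS rates at fixed times (6 and 12 months are the examples) are also estimated with 95% CIs. No hazard ratio, difference in OS rates or other comparison appears in the visible text. The section says in so many words that results are given by arm only for disease control rate. For PFS and OS this follows from Section 6, which summarises results by regimen received.
- **Testing.** Section 6.1: "This study is not designed to make explicit power and type I error considerations for a hypothesis test".
- **Concluding an arm.** Section 4.6.1 begins its rule "For an experimental arm, in which all patients discontinued treatment and passed the safety follow-up window". Once about 80% of that arm have also left the study, the sponsor may conclude it and discontinue the remaining 20% or so. The survival follow-up footnotes in Appendices 7 and 8 repeat the rule. None of the three places gives a matching rule for control.

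**The concern.** A randomised control arm earns its place through a comparison. The plan makes that comparison for ORR and stops short of it for the two time-to-event endpoints, where readers will look for durable benefit. With only two medians and their separate intervals, they will compare by eye. That uses the follow-up inefficiently and gives no interval for the quantity of interest.

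The protocol's own comparative evidence is reported as hazard ratios: 0.80 for OS and 0.74 for PFS in the first-line nivolumab trial (Section 1.3's background in Section 1.2), and 0.57 for PFS in the randomised tiragolumab trial in lung cancer (Appendix 8, A8-2.6.2). The corresponding figure is not planned here. If one is produced later, the model and cut-off will have been chosen after open-label data were seen.

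**Working it through.** **1. The plan's own figure.** Section 6.1: "Approximately 40-90 patients will be randomly allocated to the control and experimental arms during the study". Section 3.1.2 gives the experimental arm: "For most arms, approximately 20 patients will be enrolled during the preliminary phase", then "approximately 25 additional patients may be enrolled in that arm during the expansion phase". Section 4.2 caps the chance of allocation to control at 50%. At 1:1 the totals are 20/0.5 = 40 and (20 + 25)/0.5 = 90, so the stated range is reproduced as 20 or 45 per arm. There is no power, alpha or event target to reproduce.

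**2. Hazard ratio precision.** SE(log HR) = √(4/d) for d events split equally between arms; CI factor = exp(1.96 × SE). The documents project no event counts, so 70% to 100% is shown as an assumption.

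| Per arm | Events d | CI factor | 95% CI at observed HR 0.74 |
|---|---|---|---|
| 20 | 28 (70%) | 2.10 | 0.35–1.55 |
| 20 | 32 (80%) | 2.00 | 0.37–1.48 |
| 20 | 40 (100%) | 1.86 | 0.40–1.38 |
| 45 | 63 (70%) | 1.64 | 0.45–1.21 |
| 45 | 72 (80%) | 1.59 | 0.47–1.17 |
| 45 | 90 (100%) | 1.51 | 0.49–1.12 |

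**3. Ratio of medians.** With exponential times and no censoring before the median, SE(log ratio) = (1/ln 2) × √(2/n), n per arm.
- n = 20: 1.443 × 0.316 = 0.456, factor 2.45.
- n = 45: 1.443 × 0.211 = 0.304, factor 1.82.

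At 80% events the median comparison carries (0.354/0.456)² ≈ 60% of the information in the hazard ratio. With complete data it is (ln 2)² ≈ 48%.

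**4. Difference in OS rate.** With an exponential median of 13.8 months (the nivolumab trial, all randomised), 12-month OS = 0.5^(12/13.8) = 54.7%. Ignoring censoring, the half-width of the difference is 1.96 × √(2 × 0.547 × 0.453/n): ±20.6 points at 45 per arm and ±30.9 at 20. At 6 months (74.0%) it is ±18.1 and ±27.2.

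**5. Power, if anyone wished to test.** Two-sided 5%, power = Φ(√(d/4) × |ln HR| − 1.96). At the maximum of 90 events this is 18% for HR 0.80, 30% for 0.74 and 76% for 0.57.

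**6. Effect of the arm-conclusion rule.** Assume that all patients who left the study had died. Then 36 of 45 experimental patients have events and 9 are censored, and SE = √(1/36 + 1/45) = 0.224 against √(1/45 + 1/45) = 0.211. The CI factor moves from 1.51 to 1.55; at 20 per arm (16 v 20 events) it moves from 1.86 to 1.93. Exponential survival reaches 80% deaths at median × ln 5/ln 2: 26.9 months for a median of 11.6 and 32.0 months for 13.8. Both fall after the median and after the 6- and 12-month time points.

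**The case against.** The strongest reply is that this is a signal-finding study which openly declines to plan for a test, and that any PFS or OS contrast would be too imprecise to act on. The first half stands: step 5 shows that a test would be weak, and its absence is a declared choice, not a defect. But Section 6.1 disclaims power and type I error, not estimation, and ORR already receives an estimate with an interval. Imprecision is a reason to print the interval, so that two medians are not over-read.

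The tiragolumab trial that reported 0.57 was also larger, at 135 patients against at most 90 or so here. That stands. Still, its interval of 0.37 to 0.90 implies a factor of √(0.90/0.37) = 1.56, close to the 1.59 at 45 per arm with 72 events. At 20 per arm the interval is clearly wider.

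Method names in Section 6.4 and all of Section 6.9 are blacked out, so a comparison in hidden text cannot be excluded. In Section 6.4.2, however, the gaps sit where method names belong and the sentences around them are complete.

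A reader might infer more than the documents support:
- **That only medians are planned.** This is true of PFS. OS also has rates at fixed times.
- **That the arm-conclusion rule removes the contrast or makes the OS curves incomparable.** The contrast is missing because Section 6.4.2 specifies none. The rule is optional and needs every patient off treatment and about 80% off study. Under step 6 it trims the late tail. Censoring that differs by arm is compatible with a hazard ratio if it is non-informative.
- **That the patients cut off are the longest-followed survivors.** They are whoever remains. Section 4.6.2 counts withdrawal and loss to follow-up as leaving the study, so late enrollees may be among them.
- **That the trial cannot report a hazard ratio.** It does not plan one, but nothing prevents it.

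**Conclusion.** The point holds as a missing estimate, not a missing test. The visible plan compares the arms on ORR but not on PFS or OS, although the design supports all three. At 80% events a hazard ratio narrows the CI factor from 2.45 to 2.00 at 20 per arm, and from 1.82 to 1.59 at 45 per arm. These figures rest on exponential times, 1:1 allocation and an assumed event fraction. The gain is useful but leaves a wide interval, so this is an inexpensive improvement to a descriptive plan.

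The one-sided arm-conclusion rule is separate and minor. If the exits are deaths, it changes the OS CI factor by a few hundredths. If many are withdrawals, the loss is larger and could come earlier; the documents give no split.

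**What to change.** In Section 6.4.2, add for PFS and OS a Cox hazard ratio with 95% CI, experimental against concurrently randomised control. Add the between-arm difference in OS rate at 6 and 12 months with 95% CI, which does not rely on proportional hazards. Label all of these as estimation without a hypothesis test.

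State that the OS contrast uses one common clinical cut-off date for both arms, so that concluding the experimental arm under Section 4.6.1 does not leave unequal follow-up in the comparison.

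The cost is plan wording and a few standard outputs, with no extra patients. The published interval will be wide and should be shown as such. With a common cut-off, any later control follow-up is left out of that contrast, though it can still be reported for the control arm alone.
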